5.1.2 Cohort E

The primary endpoint for the expansion part cohort E is objective response (OR).

Objective response (OR)

OR is defined as best overall response of complete response (CR) or partial response (PR), where best overall response is determined according to Response Evaluation Criteria In Solid Tumours (RECIST) version 1.1 from date of first treatment administration until the earliest of disease progression, death or last evaluable tumour assessment before start of subsequent anti-cancer therapy.

Best overall response

An adequate RECIST tumour assessment includes an assessment of target lesions (only for patients with measurable disease at baseline), as well as radiological tests to evaluate non-target lesions if any and to search for new lesions. In case no RECIST tumour evaluation has been performed, the assessment will be set to missing.

Best overall response is calculated based on the “overall” visit response from each assessment. Best overall response represents the best response a patient has had during his/her time in the study until progression, last evaluable assessment in the absence of progression or the start of subsequent anti-cancer therapy. For patients whose progression event is death, best overall response will be calculated based on data until the last evaluable RECIST assessment prior to death. (note that no confirmation is required for best overall response)

The following categories of best overall response will be derived:

- Complete response (CR)
- Partial response (PR) – possible only for patients with measurable disease at baseline
- Stable disease (SD) – possible only for patients with measurable disease at baseline

Proprietary confidential information © 2021 Boehringer Ingelheim International GmbH or one or more of its affiliated companies

- Subcategory “SD \geq Week 24” for breast cancer and “SD \geq 6 weeks” for NSCLC: calculated from randomization/treatment start until the earliest of disease progression, death or last evaluable tumour assessment before start of subsequent anti-cancer therapy. Here SD \geq Week 24 includes SD \geq 161 days taking into account allowable CTP window.
- Non-CR/Non-PD – possible only for patients with non-measurable disease at baseline
 - Subcategory “Non-CR / Non-PD \geq Week 24” for breast cancer and “Non-CR / Non-PD \geq 6 weeks” for NSCLC: calculated from randomization/treatment start until the earliest of disease progression, death or last evaluable tumour assessment before start of subsequent anti-cancer therapy. Here Non-CR / Non-PD \geq Week 24 includes Non-CR / Non-PD \geq 161 days taking into account allowable CTP window.
- Progressive disease (PD) in the absence of CR or PR or SD or Non-CR/Non-PD
- Not evaluable (NE) - means no evidence of CR or PR or SD or Non-CR/Non-PD or PD
 - Subcategory ‘Missing post-baseline image’: in case no post-baseline image has been performed.

The Week 24 tumour assessment was chosen to coincide with the minimum required duration of SD or Non-CR/Non-PD (24 weeks), in order to include all Week 24 assessments allowable per protocol the cut-off of \geq 161 days has been implemented.

5.1.3 Cohorts D1 and D2

The primary endpoint for expansion part cohort D1 and D2 is Progression-free survival (PFS) status at 18th month (PFS18).

PFS18 is defined as the PFS status of a patient who is alive without disease progression at 18 months after first treatment administration, where progression is determined according to RECIST 1.1.

PFS is defined as the time from first treatment administration until tumour progression according to RECIST 1.1 or death from any cause, whichever occurs earlier.

Tumour assessments will be performed at screening and then every 8 weeks after start of the first treatment course until week 48 and every 12 weeks thereafter.

For each follow-up imaging time-point an overall tumour response will be determined according to RECIST 1.1. The overall tumour response for each imaging time-point will be selected from the following categories: Complete Response (CR); Partial Response (PR); Stable Disease (SD); Progressive Disease (PD); Non-CR/Non-PD; or Not Evaluable (NE).

For details on the imaging process and RECIST evaluation, see Section 5.2 and Section 10.4 of the CTP.

Derivation of endpoint PFS

Derivations below are described in days. However, the endpoints below will be presented in months in the statistical tables produced for the Clinical Trial Report (CTR).

Proprietary confidential information © 2021 Boehringer Ingelheim International GmbH or one or more of its affiliated companies

For patients with 'event' as an outcome for PFS: (according to RECIST version 1.1)

- PFS [days] = date of outcome - date of the first treatment administration + 1.

For patients with 'censored' as an outcome for PFS: (according to RECIST version 1.1)

- PFS (censored) [days] = date of outcome - date of the first treatment administration + 1.

The censoring rules for PFS (i.e. outcome and date of outcome) are given in [Table 5.1.3:1](#). Clinical disease progression will not be considered for determination of a PFS event, unless the outcome of the progression is death.

If patients would have their radiological examinations over a number of days, i.e. target lesions assessed on day x, non-target lesions assessed on day y and new lesion (if applicable) on day z, the following rules will be applied:

- If the overall response is PD, the earliest date of multiple assessments will be taken.
- If the overall response is SD, Non-CR/Non-PD, PR, CR or NE, the latest of multiple assessment dates will be taken to censor the patients.

Imaging assessments for which NE is assigned as the overall response at an imaging time-point are considered to be missed assessments. Please note that NE does not indicate lack of progression.

Table 5.1.3: 1 Derivation rules for PFS

Situation	Outcome (event or censored)	Date of outcome
No baseline radiological assessment		
Patient with death on or before the second planned radiological assessment	Event	Date of death
Patient without death or patient with death after second performed radiological assessment	Censored	Date of randomisation (or first treatment administration, in non-randomised trials)
Without post-baseline radiological assessments		
Vital status is unknown or patient is known to be alive	Censored	Date of randomisation (or first treatment administration, in non-randomised trials)

Proprietary confidential information © 2021 Boehringer Ingelheim International GmbH or one or more of its affiliated companies

Situation	Outcome (event or censored)	Date of outcome
Death prior or on the second planned radiological assessment	Event	Date of death
Death beyond the second planned radiological assessment	Censored	Date of randomisation (or first treatment administration, in non-randomised trials)
With baseline and post-baseline radiological assessments BUT no other anti-cancer therapy		
Alive and not progressed, no more than one consecutively missed radiological assessments	Censored	Date of last radiological assessment
Alive and not progressed, two or more consecutively missed radiological assessments	Censored	Date of last radiological assessment prior to missed radiological assessments
Progressed, zero or one missed radiological assessment prior to progression	Event	Date of radiological assessment of progression
Progressed, but two or more consecutively missed radiological assessments prior to progression	Censored	Date of last radiological assessment prior to missed assessment
Death but no progression, zero or one missed radiological assessment prior to death	Event	Date of death
Death without progression, but two or more consecutively missed radiological assessments prior to death	Censored	Date of last radiological assessment prior to missed assessments

Proprietary confidential information © 2021 Boehringer Ingelheim International GmbH or one or more of its affiliated companies

Situation	Outcome (event or censored)	Date of outcome
Initiation of subsequent anti-cancer therapy		
Subsequent anti-cancer therapy started before progression or death	Censored	Date of last radiological assessment before subsequent anti-cancer therapy
No baseline and/or post-baseline imaging and subsequent anti-cancer therapy started prior to a death	Censored	Date of randomisation (or first treatment administration, in non-randomised trials)

In order to identify that consecutive imaging time-points are missing for a given patient, a nominal time point [8, 16, 24, 32, 40, 48, and then every 12 weeks thereafter] will be assigned to each and every image. This is achieved by creating windows for every RECIST assessment. The windows are defined in [Table 6.7.2: 1](#).

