Progressed, zero or one missed radiological assessment prior to progression	Event	Date of radiological assessment of progression
Progressed, but two or more consecutively missed radiological assessments prior to progression	Censored	Date of last radiological assessment prior to missed assessments
Death but no progression, zero or one missed radiological assessment prior to death	Event	Date of death
Death without progression, but two or more consecutively missed radiological assessments prior to death	Censored	Date of last radiological assessment prior to missed assessments
Initiation of subsequent anti-cancer therapy		
Subsequent anti-cancer therapy started before progression or death	Censored	Date of last radiological assessment before subsequent anti-cancer therapy
No baseline and/or post-baseline imaging and subsequent anti-cancer therapy started prior to a death	Censored	Date of randomisation (or first treatment administration, in non-randomised trials)

[figure not shown]
Progression-free survival (PFS)The derivation of endpoint PFS refers to [Section 5.1.3](#).Last evaluable imaging

Proprietary confidential information © 2021 Boehringer Ingelheim International GmbH or one or more of its affiliated companies

[figure not shown]
An evaluable radiological image for the censoring of PFS is an image for which an overall response assessment of SD, Non-CR/Non-PD, PR or CR has been assigned. This is used for censoring of patients without progression at end of trial, or censoring prior to missed assessments, or censoring prior to subsequent anti-cancer therapy

Objective response (OR) (Cohorts F, D1 and D2 only)

[figure not shown]
The definition for OR is the same as the primary endpoint for cohort E , refer to [Section 5.1.2.](#)

[figure not shown]
Proprietary confidential information © 2021 Boehringer Ingelheim International GmbH or one or more of its affiliated companies

[figure not shown]
Proprietary confidential information © 2021 Boehringer Ingelheim International GmbH or one or more of its affiliated companies

[figure not shown]
Proprietary confidential information © 2021 Boehringer Ingelheim International GmbH or one or more of its affiliated companies

Proprietary confidential information © 2021 Boehringer Ingelheim International GmbH or one or more of its affiliated companies

Proprietary confidential information © 2021 Boehringer Ingelheim International GmbH or one or more of its affiliated companies

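### SAP 5.1.3 lists not-evaluable (NE) assessments among those whose date censors PFS, against its own next sentence and SAP 5.2.2.2: a minor error, wrong as written

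*SAP*

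**What the plan says.** PFS status at month 18 (PFS18) is the primary endpoint of cohorts D1 and D2. SAP 7.4.3 reports it as a number and percentage of treated patients and also tabulates the Kaplan-Meier estimate at 18 months. Protocol 7.3.1 specifies Kaplan-Meier.

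Five places in the SAP bear on the censoring date:

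- **SAP 5.1.3, source of the rules.** "The censoring rules for PFS (i.e. outcome and date of outcome) are given in" Table 5.1.3:1.
- **SAP 5.1.3, dating bullets.** These are introduced by "If patients would have their radiological examinations over a number of days". If the overall response is PD, the earliest date is used. For the rest: "If the overall response is SD, Non-CR/Non-PD, PR, CR or NE, the latest of multiple assessment dates will be taken to censor the patients".
- **SAP 5.1.3, next sentences.** "Imaging assessments for which NE is assigned as the overall response at an imaging time-point are considered to be missed assessments". Then: "Please note that NE does not indicate lack of progression".
- **Table 5.1.3:1.** The row "Alive and not progressed, no more than one consecutively missed radiological assessments" censors at the date of the last radiological assessment. The word evaluable does not appear.
- **SAP 5.2.2.2, last evaluable imaging.** The definition lists the responses that qualify: "An evaluable radiological image for the censoring of PFS is an image for which an overall response assessment of SD, Non-CR/Non-PD, PR or CR". NE is not on that list. On its use, the SAP says: "This is used for censoring of patients without progression at end of trial", and it adds censoring before missed assessments and before subsequent anti-cancer therapy.

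SAP 6.7.2 separately calls an assessment missed when the patient has no image in the window.

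**The concern.** The same date cannot be both taken to censor and excluded from censoring. The bullet says the first of an NE assessment; SAP 5.2.2.2 says the second.

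Table 5.1.3:1 ought to decide, but it does not. A single final NE scan counts as one missed assessment, so the row for no more than one missed assessment applies. That row points to the last radiological assessment, and an NE scan is literally a radiological assessment. For best overall response (SAP 5.1.2) the SAP does write that the last tumour assessment must be evaluable, so the omission in the table is noticeable. SAP 6.7.2 adds to the doubt: an NE scan is an image in the window, so by that definition it is not missed, whereas by 5.1.3 it is.

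At stake is the censoring date in the primary-endpoint derivation. A later date resting on an NE scan adds progression-free time that no image supports. If that date falls after month 18, it could change how the patient is classified in the PFS18 count.

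**Working it through.** **1. The plan's imaging windows.** SAP Table 6.7.2:1 gives due day = week × 7 + 1, with bounds at the midpoints between due days.
- Week 60 (check): due 60 × 7 + 1 = 421; lower bound (337 + 421)/2 + 1 = 380; upper bound (421 + 505)/2 = 463. This matches the table.
- Week 72, same rule: due 505; window 464 to 547.
- Week 84, same rule: due 589; window (505 + 589)/2 + 1 = 548 to (589 + 673)/2 = 631.

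**2. Month 18 in days.** SAP section 7 sets months = days × 12 ÷ 365.25, so 18 months = 18 × 365.25/12 = 547.875 days. The week-72 window closes on day 547 and the week-84 window opens on day 548. Week 84 is therefore the first scheduled scan that can document status at month 18. Protocol 8.6 sets the D1/D2 milestone at 18 months of PFS observation, so for late enrollees it may also be the last scan before analysis.

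**3. Censoring date under each reading.** Assume no event, and a week-84 assessment whose latest examination date is day 589.

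| Last scans | Bullet read literally | NE treated as missed and not evaluable |
|---|---|---|
| SD at week 72, NE at week 84 | day 589 = 19.35 months | day 505 = 16.59 months |
| Evaluable at week 60, NE at weeks 72 and 84 | day 589 = 19.35 months | day 421 = 13.83 months (row for two or more missed) |

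The literal result in the second row also needs the 6.7.2 definition, under which neither NE scan is missed.

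**4. Crude PFS18 count.** Assume 30 patients, 12 events by day 505, everyone else followed to day 589, and a count that includes only patients whose event-free time reaches month 18. With one patient of the first type:
- NE date used: 18/30 = 60.0%.
- Evaluable date used: 17/30 = 56.7%.
- Difference: 1/30 = 3.3 points per such patient.

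**5. Kaplan-Meier at month 18, same data.**
- No event between day 505 and month 18: 18/30 = 60.0% under both readings, because a censored patient is not counted as a success.
- One further event at day 530, NE date used: 0.60 × (1 − 1/18) = 56.7%.
- The same event, evaluable date, one affected patient: 0.60 × (1 − 1/17) = 56.5%.
- The same event, evaluable date, three affected patients: 0.60 × (1 − 1/15) = 56.0%.

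The event pattern in steps 4 and 5 is an illustration. The documents give no count of NE final scans.

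**The case against.** The best defence is that the bullet is not the censoring rule. SAP 5.1.3 assigns outcome and date to Table 5.1.3:1. The bullet only picks one date when target, non-target and new-lesion examinations fall on different days. An NE assessment may need a date for window assignment, although the SAP does not give that reason. The next sentence classes NE as missed, and the 5.2.2.2 definition is expressly for PFS censoring. Read together, these give day 505 in the example; day 589 arises only if a programmer follows the bullet against both.

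Most of this stands, and it limits the point to a wording error with a narrow trigger. It does not remove the conflict. The bullet says the date is taken to censor, not to assign a window. The evaluable-image definition sits under the secondary endpoints, and 5.1.3 does not refer to it. The use it names for patients without progression is the end of the trial, whereas Protocol 7.3 allows the expansion-cohort primary analysis before the end of the study. Patients still ongoing at such a cut are not plainly covered.

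A reader might also turn to protocol Table 7.7:2 and infer that a 3-point shift changes the D1 operating characteristics, since moving from 0.57 to 0.60 takes 0.08 to 0.04 (true rate 43%) and 0.62 to 0.51 (true rate 60%). That does not follow. The columns are thresholds for the observed rate, so this move is to a stricter threshold and the probabilities fall. An inflated estimate against a fixed threshold would work in the opposite direction.

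**Conclusion.** Wrong as written; minor. The bullet in SAP 5.1.3 contradicts the sentence that follows it and SAP 5.2.2.2, and neither Table 5.1.3:1 nor SAP 6.7.2 resolves the conflict.

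The size is limited. An effect on PFS18 of the kind shown needs an NE assessment on or after day 548, no evaluable scan from then on, and literal programming of the bullet. Each such patient could then add 3.3 points to the crude percentage in a 30-patient cohort, on the counting assumption stated in the working. In the illustration the Kaplan-Meier rate is unchanged, or about 0.2 points higher for one patient and 0.7 for three when an event falls between the two dates.

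A reader might infer that the plan sets out to credit patients as progression-free at month 18 on scans that show nothing. The documents do not support that: SAP 5.1.3 itself warns that NE is not evidence of lack of progression, and the rules taken together favour excluding NE dates. The analyses are also descriptive, with no formal test (Protocol 7.2).

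**What to change.** - In SAP 5.1.3, delete NE from the censoring bullet, or state that the date of an NE assessment is used only to assign it to an imaging window.
- In Tables 5.1.3:1, 5.2.2.2:1 and 5.2.2.2:2, change the date column to the last evaluable radiological assessment. The two duration tables need this in their own right, because the evaluable-image definition is worded for PFS.
- Cross-reference that definition in 5.1.3, so that it visibly governs PFS18 at any analysis cut.
- A short note in 6.7.2 that an image rated NE counts as missed would close the remaining gap.

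The cost is SAP wording only, with no new data. Compared with a literal reading of the bullet, a few censoring times become shorter.

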7.3.1 Primary endpoint analyses

For dose finding cohorts A, B, C, and D (dose finding):

In order to identify the MTD, the number of patients with DLTs during the MTD evaluation period at each dose level will be presented. Patients who discontinue during the first treatment course for reasons other than DLT will be excluded from the determination of MTD.

For expansion cohort E:

Objective response will be analysed in terms of objective response rate, defined as the proportion of patients with best overall response of CR or PR (note that no confirmation is required for best overall response).

For cohorts D1 and D2:

PFS rate at 18th month will be derived using Kaplan Meier method. Cohort D1 for visceral vs. cohort D2 for non-visceral will be displayed separately. The details will be described in the TSAP.

For expansion cohort F

DC will be analysed in terms of DC rate, defined as the proportion of patients with best overall response of CR, PR, SD lasting for at least 24 weeks or non-CR/non-PD lasting for at least 24 weeks.

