7.4.3 Cohorts D1 and D2

PFS status at 18th month (PFS18)

PFS18 is defined as the PFS status of a patient who is alive without disease progression at 18 months after first treatment administration, where progression is determined according to RECIST 1.1.

Descriptive statistics including number of treated patients, number of patients being absence of disease progression or death at 18th month and the corresponding percentages will be presented and evaluated.

Kaplan-Meier (KM) estimates will be used to display the distribution of PFS for cohort D1 and D2 separately on a KM curve. To support the plot, estimated survival probabilities at specific time points of interest (6 months, 12 months and 18 months) will be tabulated. In addition, the survival distribution will be used to provide estimates of the median, 25th and 75th percentiles.

Proprietary confidential information © 2021 Boehringer Ingelheim International GmbH or one or more of its affiliated companies

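### SAP Table 5.1.3:1 censors some D1/D2 patients whose month-18 outcome is already known to be failure, and no visible sensitivity analysis tests the effect

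*SAP*

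**What the plan says.** SAP 5.1.3 sets the endpoint as a status: "PFS18 is defined as the PFS status of a patient who is alive without disease progression at 18 months after first treatment administration". The same section defines PFS as time to "tumour progression according to RECIST 1.1 or death from any cause, whichever occurs earlier". Protocol 5.1.1 describes the D1/D2 primary endpoint in the same sense, and SAP 4.2 records no change from the protocol.

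Table 5.1.3:1 then gives the derivation rules. Three rows matter here:

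- No post-baseline scan, "Death beyond the second planned radiological assessment": censored at first treatment administration, so PFS is 1 day. The companion row, "Death prior or on the second planned radiological assessment", is an event at the date of death.
- "Progressed, but two or more consecutively missed radiological assessments prior to progression": censored at the last scan before the gap.
- "Death without progression, but two or more consecutively missed radiological assessments prior to death": censored at the last scan before the gap.

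A scan read as not evaluable counts as missed.

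On estimation, Protocol 7.3.1 says "PFS rate at 18th month will be derived using Kaplan Meier method". SAP 7.4.3 says the "number of patients being absence of disease progression or death at 18th month and the corresponding percentages will be presented and evaluated", with Kaplan-Meier estimates at 6, 12 and 18 months tabulated alongside. It does not say how a patient censored before month 18 enters that percentage. Protocol 7.3.2 leaves the PFS censoring rules to the SAP.

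**The concern.** Censoring after missed scans is normally justified by doubt about when the event happened. That reason is weak for a fixed-time status. If a progression or death is documented before month 18, the patient has failed by month 18 whatever the exact date, and a date of death is not in doubt.

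The day-1 rule is also abrupt. Taking week 16 at its due date (16 × 7 + 1 = day 113), a death without post-baseline imaging is an event on day 113 and is censored back to day 1 on day 114. The week-16 window in Table 6.7.2:1 runs to day 141.

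D1 and D2 are single-arm cohorts read against planning rates, so no control arm absorbs a shift caused by censoring. Gaps are possible: the current Protocol 5.2 leaves tumour assessment to institutional practice, while the SAP keeps fixed 8- and 12-week windows. The documents do not say how many patients this affects.

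**Working it through.** **Inputs.** N = 30 per cohort, 20% dropout, the assumed true rates and the probabilities in Tables 7.7:2 and 7.7:3 come from Protocol 7.7. Day 113 comes from SAP 6.7.2. Month 18 = 18 × 365.25 / 12 = 547.9 days (SAP 7). The share of events recoded is an **assumption**: 5%, 10% or 20% of events between day 113 and month 18. At a true 43%, about 12.3 of 30 patients have an event in that interval (exponential PFS), so this means roughly 0.6 to 2.5 patients.

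**Step 1: the plan's own figures.** Simulated Kaplan-Meier estimate at month 18, exponential PFS, 20% exponential dropout by month 18, 60,000 trials:

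| Cohort, threshold | True rate | Plan | Reproduced |
|---|---|---|---|
| D1, >57% | 60% | 0.62 | 0.628 |
| D1, >57% | 43% | 0.08 | 0.074 |
| D2, >65% | 69% | 0.68 | 0.676 |
| D2, >65% | 52% | 0.10 | 0.091 |

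The largest gap over all 30 table cells is 0.014. Reading the dropout as 20% per 12 months fits equally well (largest gap 0.015). An exact binomial without dropout does not fit: at least 18/30 gives 0.578 and 0.046, and at least 17/30 gives 0.715 and 0.093, for D1. The planning figures therefore behave as Kaplan-Meier with independent dropout only. They include no recoding of events as censored.

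**Step 2: direction for one recoded event.** With d true events by month 18, k of them censored at day 1 and no other censoring, the Kaplan-Meier estimate is (N − d)/(N − k).

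- d = 17: 13/30 = 43.3%; for k = 1, 2, 3: 13/29 = 44.8%, 13/28 = 46.4%, 13/27 = 48.1%.
- d = 12: 18/30 = 60.0%; for k = 1, 2, 3: 18/29 = 62.1%, 18/28 = 64.3%, 18/27 = 66.7%.

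The values of k are illustrative.

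**Step 3: size with dropout.** Assumed share of day 113 to month 18 events censored three scheduled scans back:

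| Cohort, true rate | 5% | 10% | 20% |
|---|---|---|---|
| D1 0.43: mean estimate | 0.443 | 0.454 | 0.480 |
| D1 0.43: P(>57%) | 0.10 | 0.12 | 0.19 |
| D1 0.60: mean estimate | 0.612 | 0.621 | 0.644 |
| D2 0.52: mean estimate | 0.532 | 0.544 | 0.569 |
| D2 0.52: P(>65%) | 0.115 | 0.143 | 0.212 |

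If the same events are instead censored at day 1, D1 at 0.43 gives means of 0.439, 0.449 and 0.471, and P(>57%) of 0.09, 0.11 and 0.17.

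**Step 4: when the shift disappears.** If the day-1 rule also removes patients whose event falls after month 18, at the same 20% rate, the D1 mean at a true 0.43 moves only from 0.431 to 0.433.

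**Step 5: the SAP 7.4.3 percentage.** With three of 17 events recoded, counting only patients known to be event-free over all treated leaves 13/30 = 43.3%. Reading the percentage as one minus coded events over treated gives 1 − 14/30 = 16/30 = 53.3%. The text does not settle which applies.

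**The case against.** The rules are openly declared, sit in the same section as the definition, and were delegated to the SAP by the protocol. They govern the time-to-event variable. PFS18 is defined separately as a status, and nothing in SAP 7.4.3 says that a patient known to be dead is counted as event-free. A reader might infer that the table flatly contradicts the endpoint. The documents support less: an inconsistency for patients with a known failure, and silence on how censored patients enter the percentage.

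A reader might also infer that the rules always push the rate up, or that every death without imaging is lost at day 1. Neither holds. Deaths up to the second planned assessment are events. The table also censors event-free patients early when they miss scans, and Steps 4 and 5 show that the net shift can vanish.

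Recoding only the event patients would create a bias of its own. Suppose 13 of 30 are event-free, and gaps with censoring near day 1 affect three event and two event-free patients (assumed counts). The existing table gives 11/25 = 44.0%, a one-sided correction gives 11/28 = 39.3%, and the truth is 43.3%. This objection stands, and it is why the remedy must be symmetric.

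Finally, Protocol 7.2 plans no formal test, so no pass/fail decision changes. Parts of the SAP are blacked out, so the absence of a sensitivity analysis can be stated only for the visible text.

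**Conclusion.** The concern holds in a limited form. For patients with documented progression or death before month 18 who fall under the three rows, the derivation is inconsistent with the PFS18 status, and each such recoding raises the Kaplan-Meier estimate. On the assumed 5–20% recoding of events between day 113 and month 18, the shift is about 1 to 5 points. With censoring three scans back, the D1 chance of exceeding 57% at a true 43% rises from about 8% to about 10–19%, and the D2 chance of exceeding 65% at a true 52% rises from about 10% to about 12–21%. These are descriptive probabilities, not a type I error rate. They assume exponential PFS and recoding confined to patients with an event before month 18. The stronger conclusion, that the reported primary rate will be inflated, is not supported, because the documents do not show who misses scans or how many.

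**What to change.** Keep Table 5.1.3:1 for the main curve if wished, and add two things to the SAP.

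1. For D1 and D2, pre-specify a sensitivity analysis of the 18-month rate that ignores missed-scan gaps in both directions. Every documented progression or death by month 18 is an event at its date, regardless of missed or absent imaging. Event-free patients with a later evaluable scan are followed to their last evaluable scan. In the example above, if both event-free patients had an evaluable scan past month 18, this returns 13/30 = 43.3%.
2. In 7.4.3, state that a patient with documented progression or death before month 18 is never counted as event-free in the PFS18 percentage, and say how other patients censored before month 18 enter it.

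The cost is one paragraph and one extra table, with no new data. The estimate may come out slightly less favourable.
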